#### Noncompliance

- \_\_\_ 20. Prospective participants who, in the opinion of the investigator, may not be able to comply with all study procedures (including compliance issues related to feasibility/logistics).

### **3.3 Inclusion of Women and Minorities**

The study is open to anyone regardless of gender or ethnicity. Efforts will be made to extend the accrual to a representative population, but in a trial which will accrue approximately 25 participants, a balance

must be struck between participant safety considerations and limitations on the number of individuals exposed to potentially toxic or ineffective treatments on the one hand and the need to explore gender, racial, and ethnic aspects of clinical research on the other. If differences in outcome that correlate to gender, racial, or ethnic identity are noted, accrual may be expanded or additional studies may be performed to investigate those differences more fully.

## **4.0 SCREENING AND REGISTRATION PROCEDURES**

---

### **4.1 Informed Consent**

The investigational nature and objectives of the trial, the procedures and treatments involved and their attendant risks and discomforts, and potential alternative therapies will be carefully explained to the participant and a signed informed consent will be obtained. Documentation of informed consent for screening will be maintained in the participant's research chart and medical record.

### **4.2 Screening Procedures**

Diagnostic or laboratory studies performed exclusively to determine eligibility for this trial will be done only after obtaining written informed consent. Studies or procedures that were for clinical indications (not exclusively to determine study eligibility) may be used for baseline values, even if the studies were done before informed consent was obtained. See Section 10.0 – Study Calendar, for a list of screening procedures and accompanying windows for their administration.

### **4.3 Registration Requirements/Process**

Eligible patients must be registered within 2 weeks prior to start of protocol therapy.

Registration of participants is to be via completion of the following steps:

- Prospective participants must complete the informed consent process, including a signed informed consent, prior to proceeding to study screening.
- Screening procedures and windows are detailed in Section 10 and Table 10, Study Activity Calendar.
- Once all the pre-study requirements have been fulfilled, including a completed eligibility checklist, the study coordinator can register the eligible patient into MIDAS.
- Patients failing to meet all protocol eligibility criteria, including informed consent, may not be registered for the trial.

## **5.0 TREATMENT PROGRAM**

---

### **5.1 Treatment Overview**

Treatment on study will be in the outpatient setting and will consist of biweekly (every 2 weeks) treatment with panitumumab and FOLFIRI.

A treatment cycle is defined as the period starting from administration of study agents up to the subsequent administration of study agents, and thus will typically be a two week duration. Day 1 of each treatment cycle is defined as the day of treatment administration. Windows for all assessments and treatments are detailed in Section 10.

For a tabular view of the treatment, monitoring, and follow-up schedule, see study calendar in Section 10.

The study will enroll 25 evaluable participants with advanced metastatic colorectal cancer, initially enrolling 14 participants for analysis for futility, followed by an additional 11 participants if futility is not demonstrated. A definition of an evaluable participant will consist of a participant with documented *RAS wild type* and *BRAF wild type* tumor receiving at least 1 cycle of FOLFIRI + panitumumab (*RAS and BRAF* will be determined through ONCO48 testing at COH- other CLIA certified assays for these tests will be allowed).

## 5.2 Treatment Administration Including Initial Starting Doses

See Section 5.6 for required and recommended prophylaxis.

On the day of treatment administration, panitumumab is followed by concurrent administration of irinotecan and leucovorin, followed by 5-FU:

	Starting Dose	Administration
1 Panitumumab	6mg/kg	See section 8.1.9 and 8.1.10**
2 Irinotecan	180mg/m  (125-180 mg/m  )*	As per package insert and COH standard practice (e.g. diluted to 500 ml and infused over 90 min)
3 Leucovorin	400mg/m 	As per package insert and COH standard practice.
4 5-FU	2400mg/m  (1800-2400 mg/m  )*	As per package insert and COH standard practice. Over 46 hours.

\*The treating physician may initiate irinotecan and 5-FU at attenuated doses within the indicated ranges to take into account the participant's history of prior dose-reductions for these agents. A clear justification for the lower starting dose should be documented.

\*\*The panitumumab dose will be calculated based on the participant's actual body weight at baseline and re-calculated at subsequent doses per institutional guidelines. At a minimum, the dose will be re-calculated if the actual body weight changed by at least  $\pm 10\%$  from the last time the dose was calculated.

Modifications to the doses of all agents are detailed in Section 6.2.1 and 6.2.2. Panitumumab dose levels are detailed in Table 6.2.1.

## 5.3 Planned Duration of Therapy

Participants will receive study treatment until disease progression or other criteria for study removal are satisfied.

## 5.4 Criteria for Removal from Treatment

Participants may be removed from treatment for any of the following reasons:

- evidence of disease progression
- the participant is deemed intolerant to study treatment because of toxicity, despite dose modification and delay
- participant's request
- participant deemed non-compliant by the investigator

## 5.5 Participant Follow-Up

Participants will be evaluated as detailed in the study calendar in Section 10. Once taken off study treatment, participants will be asked to provide research blood samples three times at three month intervals. The clinical study coordinator will continue to collect outcome data every 3 months through chart review or by participant outcome to collect survival data. Windows and assessments are detailed in Section 10.

## 5.6 Supportive Care, Other Concomitant Therapy, Prohibited Medications

Supportive medications as deemed appropriate by the investigated regimen will be allowed. Additional guidelines are provided in the sections that follow:

### 5.6.1 Prohibited Medications

Participants must be instructed not to take any additional medications (including over-the-counter products) during the trial without prior consultation with the investigator. All medications taken within 30 days of start of study treatment should be recorded. If concomitant therapy must be added or changed, including over-the-counter medications or alternative therapies, the reason and name of the agent/therapy should be recorded.

In general, the use of any concomitant medication/therapies deemed necessary for the care of the participant are allowed, including drugs given prophylactically (e.g. antiemetics) with the following exceptions:

- No other investigational therapy should be given to participants
- No anticancer agents other than the study medications administered as part of this study protocol should be given to participants. If such agents are required for a participant then the participant must first be withdrawn from the study.
- Co-medication that may interfere with study results; e.g. immuno-suppressive agents other than corticosteroids, such as systemic cyclosporine and tacrolimus are prohibited during the treatment phase of the study, unless discussed with principal investigator felt to be of low clinical risk to the participant.
- Use of herbal medications may have unknown interactions with the metabolism of the study agents, and therefore are prohibited from use during the treatment phase of the trial.
- Use of drugs known to **inhibit** UGT1A1, such as Atazanavir, Gemfibrozil, Indinavir, or Ketoconazole, are prohibited while undergoing study treatment as they are likely to increase SN-38 levels and increase overall toxicity to irinotecan.
- Strong CYP3A4 Inducers and Strong CYP3A4 Inhibitors (Table 5.6) are **discouraged but not prohibited**. Concomitant use of CYP3A4 hepatic-enzyme inhibitors and inducers can result in increased and decreased blood levels of irinotecan or SN-38. These agents will be allowed if deemed clinically necessary with no reasonable alternatives. If over the course of study treatment the participant receives any of these drugs, efforts should be made to discontinue the use of inhibitors or potent inducers as soon as possible. Such participants may continue study treatment only at the **discretion of the principal investigator**.

**Table 5.6 CYP3A4 Inhibitors and Inducers**

Strong CYP3A4 Inhibitors (≥5-fold increase in AUC)	Strong CYP3A4 Inducers	
Atazanavir*	Aminoglutethimide	Nevirapine
Clarithromycin	Bexarotene	Oxcarbazepine
Indinavir*	Bosentan	Phenobarbital
Itraconazole	Carbamazepine	Phenytoin
Ketoconazole*	Efavirenz	Primidone
Nefazodone	Fosphenytoin	Rifabutin
Nelfinavir	Griseofulvin	Rifampin
Ritonavir	Modafinil	Rifapentine
Saquinavir	Nafcillin	St. John's wort
Telithromycin		
Suboxone		

\*Drug is prohibited because known to inhibit UGT1A1

### 5.6.2 Hematopoietic Growth Factors and Blood Transfusions

The use of growth factors and blood transfusions will be allowed, as deemed necessary by the treating physician.

### 5.6.3 REQUIRED Anti-emetics

For FOLFIRI administration, participants will be pre-medicated by 5-HT3 inhibitor and dexamethasone. Additional anti-emetics will be provided as deemed necessary by the treating physician and may be guided by the participant's prior history.

### 5.6.4 RECOMMENDED Preemptive management of panitumumab-associated skin toxicities is recommended:

Clinical trial data with panitumumab therapy indicate that integument and eye toxicities are consistent with what has been observed for other EGFR inhibitors. Most integument- and eye-related toxicity events were mild or moderate in intensity. For participants on panitumumab, dermatologic toxicities should be managed according to institutional standard procedures. The following is provided for reference.

Starting 24 hours before study Day 1 and continuing for at least 6 weeks:

- Skin moisturizer (eg, Lubriderm), apply to face, hands, feet, neck, back, and chest daily in the morning upon rising,
- Sunscreen (para-aminobenzoic acid [PABA] -free, sun protection factor (SPF) 15 or higher, UV-A, and UV-B protection) apply to exposed skin areas before going outdoors,
- Topical steroid (1% hydrocortisone cream) apply to face, hands, feet, neck, back, and chest at bedtime, and
- Oral antibiotic (such as doxycycline 100 mg twice a day) [since doxycycline is a tetracycline derivative, participants should avoid long exposure to direct sunlight or ultraviolet light. Such exposure may result in participants experiencing an exaggerated sunburn reaction (skin erythema). Doxycycline should not be used in participants with a history of hypersensitivity to doxycycline or tetracycline]

The optimal duration of pre-emptive skin treatment is not known and, if implemented, should be individually tailored for each participant. Participants who subsequently experience skin toxicities  $\geq$  grade 2 should be managed appropriately according to the institution's standard procedures.

Examples of various alternative or complementary treatment options suggested in the literature include the following (Perez-Solar and Saltz, 2005; Segaerts and Van Cutsem, 2005; Lynch et al, 2007):

- Avoidance of sun exposure: use of sunscreen with a high SPF that blocks both UV-A and UV-B and wearing a hat
- Prophylactic use of alcohol-free emollient creams and moisturizers to combat dryness (xerosis)
- Topical hydrocortisone (1% or 2.5%) cream and/or Clindamycin 1% gel for mild cases (grade 1); tetracycline oral antibiotics for more severe ( $\geq$  grade 2) cases along with the topical treatments for grade 1 events, and use of an oral antihistamine for itch is recommended
- IV antibacterial or antifungals, as clinically appropriate, for superinfection

#### 5.6.5 **RECOMMENDED** Management of Diarrhea:

Use of diarrhea/cholinergic reaction prophylaxis will be provided as deemed necessary by the treating physician and may be guided by the participant's prior history.

Early (acute) Diarrhea: this will be defined as diarrhea occurring during or shortly after their irinotecan infusion. Acute irinotecan-induced diarrhea can be managed with atropine subcutaneously or intravenously as per institutional guidelines. The total dose of atropine should not exceed 1mg. In the event of irinotecan-induced acute diarrhea, atropine can be administered in a prophylactic manner in subsequent cycles.

Delayed diarrhea: irinotecan induced diarrhea typically occurs more than 24 hours after infusion of irinotecan and should be managed aggressively with anti-diarrhea agents. It is recommended that participants received 2 pills of loperamide (4 mg total) at the onset of the first loose bowel movement, followed by 1 pill of loperamide (2mg) every 2 hours until diarrhea-free for 12 hours. If diarrhea occurs at night, participants may take 2 tablets of loperamide (4mg) every 4 hours while awake.

Symptoms of diarrhea and/or abdominal cramping may occur at any time. Diarrhea should be managed aggressively (according to standard institutional practice e.g., with anti-diarrheal medications) in order to prevent dehydration and possible resulting renal insufficiency.

#### 5.6.6 Electrolytes

Electrolytes should be replenished per the discretion of the treating investigator. If hypomagnesemia is present, replacement should be managed with either oral and/or parental replacement, according to institutional practice and to the degree of hypomagnesemia present. It is recommended that the participant's serum magnesium level should be maintained within the normal range, as much as possible, during study treatment.

It is important to assess and manage serum potassium and calcium (adjusted for albumin) in participants who have concomitant hypomagnesemia. Participant's serum potassium and calcium parameters are recommended to be managed, as per local medical practice, and kept within the normal ranges, as much as possible, during study treatment.

Changes in electrolytes, even without blood urea nitrogen (BUN)/urea and/or creatinine elevation, may reflect early physiologic consequences of treatment-induced gastrointestinal toxicity. Participants with clinically significant electrolyte changes should be evaluated for dehydration and receive aggressive fluid and electrolyte replacement, if indicated.

### 5.6.7 Management of Panitumumab-associated Infusion Reaction

Infusion-related reactions include cytokine release syndromes/acute infusion reaction and allergic/hypersensitivity reactions as defined by the CTCAE version 4.0. Participants who experience any grade of infusion reaction during panitumumab administration will have the infusion stopped. Continuation of dosing will be based on the severity and resolution of the event. For grade 1 or 2 reactions, reduce the infusion rate by 50%. The infusion should be immediately stopped for grade 3 or 4 reactions. Depending on the severity and/or persistence of the reaction consider permanently discontinuing panitumumab.

## **6.0 EXPECTED TOXICITIES AND DOSE DELAYS/MODIFICATIONS FOR ADVERSE EVENTS**

---

### **6.1 Expected Toxicities**

#### 6.1.1 Panitumumab

**Per the package insert for systemic panitumab, the expected toxicities for panitumab are as follows, where the asterisk (\*) signifies a common event:**

*Eye disorders:* keratitis, ulcerative keratitis, growth of eyelashes.

*Gastrointestinal:* stomatitis/mucositis, intestinal obstruction, nausea, diarrhea, vomiting, dry mouth.

*General disorders and administration site conditions:* Infusion related reaction, fatigue, mucosal inflammation, dehydration, paresthesia.

*Infections:* paronychia\*, conjunctivitis, sepsis, fatal infections/complications including necrotizing fasciitis.

*Immune system disorders:* hypersensitivity reaction.

*Metabolism and nutrition disorders:* hypomagnesemia, hypocalcemia, hypokalemia.

*Skin and subcutaneous tissue disorders:* acneiform dermatitis\*, pruritus\*, erythema\*, rash\*, exfoliative rash\*, skin ulcer/abscess\*, acne, skin exfoliation\*, dry skin\*, nail disorder\*, skin fissure \*, Stevens-Johnson syndrome, toxic epidermal necrolysis, bullous mucocutaneous skin disease, photosensitivity.

*Respiratory:* Pulmonary fibrosis/interstitial lung disease, bronchospasm associated with infusion reaction, dyspnea associated with infusion reaction, cough, epistaxis.

*Renal:* acute renal failure associated from severe diarrhea and dehydration.

*Miscellaneous:* fever associated with infusion reaction, chills associated with infusion reactions hypotension associated with infusion reaction.

#### 6.1.2 Irinotecan

A list of the adverse events and potential risks associated with the irinotecan, as determined by the Irinotecan Hydrochloride Package Insert follows (\* signifies occurs in > 30%):

*Blood and lymphatic disorders:* febrile neutropenia.

*Gastrointestinal:* abdominal pain\*, constipation\*, diarrhea with early onset\*, diarrhea with late onset\*, anorexia\*, nausea, vomiting, ileus, mucositis/stomatitis, colitis, gastrointestinal bleeding, intestinal perforation, megacolon, dyspepsia.

*General disorders & administration site conditions:* asthenia\*/fatigue, fever\*, skin irritation at infusion site.

*Immune system disorders:* infusion reaction.

*Infection:* neutropenic infection, minor infection.

*Hematologic investigations:* anemia\*, eosinophilia, leucopenia\* (including lymphocytopenia), neutropenia\*, thrombocytopenia.

*Investigations-other:* increased bilirubin, increased alkaline phosphatase, increased SGOT/AST, weight loss\*.

*Metabolism and nutrition disorders:* dehydration due to gastrointestinal side effects.

*Nervous system disorders:* headache, dizziness, insomnia.

*Renal disorders:* Renal impairment/renal failure due to dehydration.

*Respiratory, thoracic and mediastinal disorders:* cough, dyspnea, interstitial lung disease.

*Skin and subcutaneous tissue disorders:* alopecia\*, rash, sweating.

*Miscellaneous:* Cholinergic reaction (associated with bradycardia, flushing, rhinitis, increased salivation, miosis, lacrimation, diaphoresis, abdominal cramping).

#### 6.1.3 Leucovorin

**As listed in the package insert the expected toxicities for oral and parenteral leucovorin are:**

*Allergic Reactions:* anaphylaxis and generalized allergic reactions

*Skin and subcutaneous tissue disorders:* hives (urticaria) associated with anaphylactoid reactions

Leucovorin with 5-FU: Leucovorin can enhance the toxicity of 5-FU. Although the toxicities observed in participants treated with the combination of leucovorin plus 5-FU are qualitatively similar to those observed in participants treated with 5-FU alone, gastrointestinal toxicities (particularly stomatitis and diarrhea) are observed more commonly and may be more severe and of prolonged duration in participants treated with the combination.

#### 6.1.4 5-Fluorouracil (5-FU)

**Per the package insert for systemic 5-FU, the expected toxicities for 5-FU are as follows, where the asterisk (\*) signifies a common event:**

*Cardiovascular:* myocardial ischemia, angina,

*Eye disorders:* photophobia, visual changes, lacrimation, lacrimal duct stenosis.

*Gastrointestinal:* stomatitis\*, esophagopharyngitis\*, diarrhea\*, anorexia\*, nausea\*, vomiting\*, gastrointestinal ulceration and bleeding.

*Hematologic:* leucopenia\* (nadir: days 9-14; recovery by day 30),, pancytopenia, thrombocytopenia, agranulocytosis, anemia.

*Immune system disorders:* anaphylaxis and generalized allergic reactions.

*Nervous system disorders:* acute cerebellar syndrome (which may persist following discontinuance of treatment), nystagmus, headache.

*Skin and subcutaneous tissue disorders:* alopecia\*, dermatitis (most commonly pruritic maculopapular rash)\*, dry skin; fissuring; photosensitivity, as manifested by erythema or increased pigmentation of the skin; vein pigmentation; palmar-plantar erythrodysesthesia syndrome, as manifested by tingling of the hands and feet followed by pain, erythema and swelling (hand-foot syndrome); nail changes (nail loss)

*Psychiatric:* disorientation, confusion, euphoria.

*Respiratory:* epistaxis.

*Miscellaneous:* thrombophlebitis.

## 6.2 Dose Modifications/Delays

### 6.2.1 General Information

1. The study will use the NCI Common Terminology Criteria for Adverse Events (CTCAE) version 4.0 to grade toxicities, except for skin- and nail-related toxicities, which must be graded using CTCAE version 4.0 with modifications found in Appendix B. A copy of the version 4.0 can be downloaded from:

<http://evs.nci.nih.gov/ftp1/CTCAE/About.html>

2. Study agents are always held together, regardless of the attribution of the toxicity.
3. There is no maximum dose reduction for irinotecan or 5-FU.
4. Panitumumab has a maximum of two dose level reductions, and will not exceed the 60% dose level according the following table:

**Table 6.2.1.4 Panitumumab Dose Reductions**

	Starting Dose	Dose Level -1	Dose Level -2
Percentage (%)	100	80	60
Panitumumab(mg/kg)	6.0	4.8	3.6

5. Dose escalation is never permitted in this study.
6. Whenever treatment is held pending resolution of toxicity to grade 1 or return to baseline, baseline values are from screening (before study treatment) assessments.
7. If the treating investigator wishes to hold the study agent(s) or dose reduce (including increasing the dose reduction) after an adverse event in a manner not outlined in Table 6.2.2, this is permissible following discussion with and written approval by the Principal investigator.\*
8. For situations where a participant experiences a toxicity which the treating investigator feels is unlikely related to treatment with either study agent, but which requires hold or reduction of either agent according to Table 6.2.2, maintaining treatment or maintaining treatment dose is allowable per discussion with and written approval by the Principal Investigator.\*
9. For holds due to toxicities related to study agent(s), if the participant does not meet criteria to resume treatment **within 28 days of last treatment** administration, the participant must permanently discontinue study treatment (all agents). However, if the participant is clearly benefiting from the study, the investigator may contact the Principal Investigator to determine if

the participant can remain on study and at what dose level. Agreement of the Principal Investigator is to be documented in writing.\*

10. For holds for reasons other than treatment related toxicities, such as inclement weather or adverse events unrelated to study agents, if the participant does not meet criteria to resume treatment within 28 days of their last administration, the study agent(s) may be restarted with written approval from the Principal Investigator, as long as there has been no significant evidence of disease progression during the treatment interruption.\*

\*The principal investigator will document assessment of the impact of these determinations on the study design, objectives and endpoints or risk to participants. If any modifications to the treatment plan might affect the study design, objectives, and endpoints, or impact the risk of participants, a single participant exception will be sought by the IRB. If the treating investigator is the principal investigator, the determination and the rationale for the determination will clearly be documented in the medical record.

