### 6.2.2 Dose Modifications

Table 6.2.2 details the criteria for disrupting treatment, dose modification and treatment discontinuation following an adverse event. See section 6.2.1 for general guidelines including the maximum number of dose reductions. The agent listed in Table 6.2.2 indicates the drug to which the toxicity is likely attributed based on the toxicity profile of the agents. For treatment purposes, the investigator will determine attribution of all toxicities.

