**Table 6.2.2 Criteria for Disrupting Treatment, Dose Modification or Discontinuation**

Adverse Event	Agent most likely attributed to toxicity	Treatment modification
Hematological Toxicities		
Thrombocytopenia Grade 1 ( $75 \times 10^9/L$ -<LLN)	Irinotecan, 5-FU	Maintain treatment
Thrombocytopenia Grade 2 ( $50 - <75 \times 10^9/L$ )		Hold all study agents until recovery to $\leq$ grade 1 (plts $\geq 75 \times 10^9/L$ ). Resume treatment with a 20% dose reduction from pre-hold dose of irinotecan and 5-FU; leucovorin and panitumumab resume at pre-hold dose.
Thrombocytopenia Grade 3 ( $25 - <50 \times 10^9/L$ )		Hold all study agents until recovery to $\leq$ grade 1 (plts $\geq 75 \times 10^9/L$ ). Resume treatment with a 20% dose reduction from pre-hold dose of irinotecan and 5-FU; leucovorin and panitumumab resume at pre-hold dose.
Thrombocytopenia Grade 4 ( $<25 \times 10^9/L$ )		Hold all study agents until recovery to $\leq$ grade 1 (plts $\geq 75 \times 10^9/L$ ). Resume treatment with a 40% dose reduction from pre-hold dose of irinotecan and 5-FU; leucovorin and panitumumab resume at pre-hold dose.
Neutropenia (ANC) Grade 1 ( $1.5 \times 10^9/L$ -<LLN)	Irinotecan, 5-FU	Maintain treatment
Neutropenia (ANC) Grade 2 ( $1.0 - <1.5 \times 10^9/L$ )		Maintain treatment

Neutropenia (ANC) Grade 3 ( $0.5 - <1.0 \times 10^9/L$ )		Hold all study agents until recovery to $\leq$ grade 2 (ANC $\geq 1.0 \times 10^9/L$ ). Resume treatment with a 20% dose reduction from pre-hold dose of irinotecan and 5-FU; leucovorin and panitumumab resume at pre-hold dose. The investigator may re-escalate to the original dose in the setting of the addition of prophylactic GCSF support.
Neutropenia (ANC) Grade 4 ( $<0.5 \times 10^9/L$ -<LLN)		Hold all study agents until recovery to $\leq$ grade 2 (ANC $\geq 1.0 \times 10^9/L$ ). Resume treatment with a 20% dose reduction from pre-hold dose of irinotecan and 5-FU; leucovorin and panitumumab resume at pre-hold dose. Consider G-CSF prophylaxis in subsequent cycles.
Anemia $\geq$ Grade 3	Irinotecan, 5-FU	Maintain treatment and manage according to BSC. If per the treating investigator anemia is not adequately managed by transfusion, hold treatment and/or apply a 20% dose reduction of irinotecan and 5-FU and continue leucovorin and panitumumab at pre-hold dose.
Serum Electrolytes		

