#### 12.3 Protocol Deviations

##### 12.3.1 Deviation Policy

This protocol will be conducted in accordance with COH's "Clinical Research Protocol Deviation Policy" located at <http://www.coh.org/dsmc/Documents/Institutional%20Deviation%20Policy.pdf>.

Deviations from the written protocol that could increase participant risk or alter protocol integrity require prior IRB approval of a single subject exception (SSE) request. In addition, if contractually obligated, the sponsor must also approve the deviation. IRB pre-approved SSE protocol modifications are considered an amendment to the protocol and not a deviation. The submission of a deviation report is not required.

Brief interruptions and delays may occasionally be required due to travel delays, airport closure, inclement weather, family responsibilities, security alerts, government holidays, etc. This can also extend to complications of disease or unrelated medical illnesses not related to disease progression.

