##### 12.3.3 Resolving Disputes

The COH Investigational Drug Service (IDS) cannot release a research agent that would cause a protocol deviation without approval by the PI. Whenever the protocol is ambiguous on a key point, the IDS should rely on the PI to clarify the issue.

In situations where there is misperception or dispute regarding a protocol deviation among the persons involved in implementing the protocol, it is the responsibility of the PI to resolve the dispute and the PI may consult with the DSMC chair (or designee) to arrive at resolution.

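### Three safety instructions (dose re-escalation, contraception period, the meaning of serious for supplier notice) are worded inconsistently and must be reconciled

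*Combined protocol and SAP*

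**What the plan says.** **(a) Re-escalation.** Section 6.2.1, item 5: "Dose escalation is never permitted in this study". Table 6.2.2, grade 3 neutropenia, after a 20% reduction of irinotecan and 5-FU: "The investigator may re-escalate to the original dose in the setting of the addition of prophylactic GCSF support". It is the only row that mentions re-escalation, and it asks for no approval. Section 6.2.2 connects the two places: "See section 6.2.1 for general guidelines including the maximum number of dose reductions".

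**(b) Contraception.** The synopsis (Summary of Eligibility Criteria) requires contraception until six months after study treatment is completed. Section 3.1, item 23, part of the checklist completed before registration, requires it until three months after study participation. The protocol does not say when participation ends.

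**(c) Serious.** Section 7.3 defines a serious adverse event by seven outcomes, the first of which is death. Section 7.5.1 sets the 10-day notice to the drug supplier for events that are serious, unexpected and suspected. A parenthesis there explains serious as every grade 3 or 4 event, plus grade 1 or 2 events that lead to hospitalization.

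**The concern.** In each pair, two people who both follow the protocol can act differently on a participant-safety instruction.

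- **(a)** Under the table row, raising a reduced dose is the investigator's decision. If item 5 governs, the same act would be a deviation. Section 12.3.2 has deviations reported to the DSMC within five days, and Section 12.3.1 says those that could increase participant risk "require prior IRB approval of a single subject exception (SSE) request".
- **(b)** Item 23 gives a length but no defined start, so no end date can be derived from it. The synopsis gives a different length from a different event.
- **(c)** Whether an unexpected, suspected death falls under the 10-day supplier rule depends on how a parenthesis is read.

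Nothing here touches the 14 + 11 = 25 participants, the interim rule or the efficacy endpoints.

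**Working it through.** The documents give no figure to reproduce on these points. The check compares the texts and adds simple arithmetic.

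**(a) Does any stated exception cover re-escalation?** Items 7 to 10 of Section 6.2.1 allow departures, each with written approval or agreement of the Principal Investigator.

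- Item 7 lets the investigator "hold the study agent(s) or dose reduce (including increasing the dose reduction) after an adverse event in a manner not outlined in Table 6.2.2". This covers holds and reductions only.
- Item 8: "maintaining treatment or maintaining treatment dose is allowable per discussion with and written approval by the Principal Investigator". This covers keeping treatment or dose unchanged.
- Item 9, for toxicity holds beyond 28 days of the last treatment, lets the Principal Investigator decide whether "the participant can remain on study and at what dose level".
- Item 10 covers restarting after holds of that length for other reasons.

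None addresses raising a reduced dose because G-CSF has been added, so item 5 and the row meet with no bridging text.

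*Size of the disputed step.* Inputs are the full starting doses in Section 5.2 (irinotecan 180 mg/m², 5-FU 2400 mg/m²) and the 20% reduction in the row.

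- Reduced doses: 180 × 0.8 = 144 mg/m² and 2400 × 0.8 = 1920 mg/m².
- Return step: 180/144 = 2400/1920 = 1/0.8 = 1.25, or +25%. The ratio is the same at any starting dose in the permitted range.
- If another 20% reduction came before, and original means the starting dose: 1/(0.8 × 0.8) = 1.56, or +56%.
- If another 20% reduction came in between (for example the grade 3 diarrhea row), and original means the dose before the neutropenia hold: also +56%, because the row sets no time limit on the return.
- If a 40% reduction came before (grade 4 thrombocytopenia row), and original means the starting dose: 1/(0.6 × 0.8) = 2.08, or +108%.

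The last three lines are illustrations, not bounds.

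**(b) Which contraception period ends later?** Let E be the months from completing treatment to the end of participation. The synopsis period ends at month 6 and the item 23 period at month E + 3. The difference is (E + 3) − 6 = E − 3, so the two agree only if E = 3.

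| Possible end of participation (visit windows ignored) | E | Item 23 ends at month | Compared with the synopsis |
|---|---|---|---|
| 30-day contact | about 1 | 4 | 2 months earlier |
| Last research draw, Table 10.0 footnote g (3 and 6 months only) | 6 | 9 | 3 months later |
| Last research draw, Table 10.0 footnote u (3, 6, 9 months) | 9 | 12 | 6 months later |
| Survival follow-up every 3 months | no stated end | no limit | later, without bound |

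Footnotes g and u contradict each other on the last draw. Sections 5.5 and 9.0 also allow three draws.

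**(c) How do the two meanings of serious differ?**

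- Section 7.3 lists death, life-threatening events, hospitalization, disability, congenital anomaly, secondary malignancy and other medically important events. It limits hospitalization to unplanned stays of at least 24 hours, or prolongation of an existing stay.
- The Section 7.5.1 parenthesis names hospitalization, without those limits, and otherwise goes by grade.
- It is wider in taking in grade 3–4 events with no serious outcome.
- It is narrower in not naming death, or grade 1–2 events that are serious for a reason other than hospitalization.
- Elsewhere the protocol separates the two ideas. Table 7.3.1 requires grade 3–4 and seriousness together and gives deaths their own rows, and a footnote to the IRB table refers to grades 3–5.

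**The case against.** **(a)** Item 5 follows a panitumumab table that only steps down from 100%, so it may mean no escalation above the starting dose. The row speaks of going back to a dose already given, and a specific row can qualify what Section 6.2.2 calls general guidelines. Section 12.3.3 adds: "Whenever the protocol is ambiguous on a key point, the IDS should rely on the PI to clarify the issue". Both readings are plausible, but neither is written, and a case-by-case clarification does not correct the text. One part of the objection does stand. A reader might infer that re-escalating is a deviation in any event. The documents do not support that, because the step is itself written into Table 6.2.2 and would be a deviation only if item 5 overrides the row. Nor can one infer that the step is always +25%.

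**(b)** The synopsis is headed a summary, and item 23 is the operative text. That does not help, because item 23 has no defined clock. A reader might infer that item 23 gives the shorter cover because three is less than six. The table above shows that this does not follow.

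**(c)** The parenthesis resembles the DSMC rows and may be shorthand. Grades 3–4 also capture some of the Section 7.3 outcomes; Appendix B, for example, describes grade 4 erythema as life-threatening or disabling. Sections 7.5 and 7.5.3 require immediate advice to the supplier on potential safety issues, and Section 7.5.4 sends it the PMT reports, at least bi-annually. These are real but partial backstops: the first rests on an undefined term and the second is periodic. The open-ended list in Section 7.5.2 has the same 10-day limit, but it is for non-SAE events, and a death fits there only if the Section 7.3 meaning is set aside. A reader might infer that fatal events would go unreported. The documents do not support that. Under Table 7.3.1 an unexpected, suspected death goes to the DSMC within 5 calendar days, and IRB reporting is unaffected. The supplier is also not the regulatory sponsor.

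**Conclusion.** The three inconsistencies are real and should be reconciled. This is a minor-to-moderate wording matter. Confidence is high that the mismatches exist and lower for their consequences.

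- **(a)** The contradiction is open as written. It reaches only participants with grade 3 neutropenia who receive prophylactic G-CSF and whose investigator chooses to re-escalate. The step is +25% after a single reduction, and more if other reductions came before or in between and the return reaches past them.
- **(b)** Both length and starting event differ, and which period ends later is undetermined.
- **(c)** This is an ambiguity with partial backstops, not a proven gap. It concerns only supplier notice of events that are both unexpected and suspected.

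The number of participants affected cannot be derived from the documents. The consent form and the supplier agreement are not available for this review and might settle (b) or (c).

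**What to change.** - **(a)** Reconcile Section 6.2.1, item 5, with the grade 3 neutropenia row, and define the original dose, including when other reductions came before or in between. Which rule should apply is for the sponsor; none is proposed here.
- **(b)** Make the synopsis and item 23 state the same length from the same defined event, and check the consent form against it. No period is proposed here. Correct footnotes g and u of Table 10.0 in the same amendment so that they agree on the number of draws.
- **(c)** Subject to the supplier agreement, state in Section 7.5.1 that any event serious under Section 7.3, including death, is notifiable when it is also unexpected and suspected. Keep the grade 3–4 events and the grade 1–2 hospitalizations listed today as an addition. Nothing now notified is dropped, and grade no longer stands as the meaning of serious.

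The cost is a few sentences in one amendment, with matching wording in the consent form and supplier agreement if needed. No analysis or sample size changes.
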